4.1.5 Concomitant Medications and Therapy

Document all concomitant medications and procedures from within 42 days prior to randomization through 2 years after the first dose of study drug.

4.1.6 Confirmation of Eligibility

Subject eligibility for enrollment will be assessed per Section 3.5. All screening procedures, unless otherwise indicated, should be completed within 42 days prior to randomization.

4.1.7 ECOG Performance Status

The ECOG performance index is provided in Appendix 2.

4.1.8 Physical Examination, Vital Signs, Height & Weight

The screening physical examination will include, at a minimum, the general appearance of the subject, height (screening only) and weight, and examination of the skin, eyes, ears, nose, throat, lungs, heart, abdomen, extremities, musculoskeletal system, nervous system, and lymphatic system.

Symptom-directed physical exams will be done during the treatment period and at the safety follow-up (SFU) visits with focus on the lymphatic system and infections.

Vital signs (blood pressure, pulse, oxygen saturation and body temperature) will be assessed after the subject has rested in the sitting position for at least 5 minutes.

4.1.9 Electrocardiogram

Subjects should be in supine position and resting for at least 10 minutes before any study-related ECGs.

4.1.10 Urine or Serum Pregnancy Test

Pregnancy tests will be required only for women of childbearing potential.

4.1.11 Hematology

Hematology studies must include complete blood count (CBC) with differential including hemoglobin, hematocrit, platelet count, ANC, and absolute lymphocyte count (ALC).

4.1.12 Serum Chemistry

Chemistry will include albumin, alkaline phosphatase, ALT, bicarbonate, blood urea nitrogen (BUN), calcium (total or ionized), chloride, creatinine, glucose, lactate dehydrogenase (LDH), magnesium, phosphate/phosphorus, potassium, sodium, total bilirubin, total protein, and uric acid. If an unscheduled ECG is done at any time, then an electrolyte panel (ie, calcium, magnesium, and potassium) must be done to coincide with the ECG testing.

4.1.13 Hepatitis B and C Testing

Hepatitis serology testing must include hepatitis B surface antigen (HBsAg), hepatitis B surface antibody (anti-HBs), anti-HBc, and HCV antibody. In addition, any subjects testing positive for any hepatitis serology must have monthly PCR testing during screening and on treatment, thereafter 3-monthly PCR for the next year.

Subjects who are anti-HBc positive should have quantitative PCR testing for HBV DNA performed during screening and monthly thereafter as per institutional practices. Any subject with a rising viral load (above lower limit of detection) should discontinue study drug and have antiviral therapy instituted and a consultation with a physician with expertise in managing hepatitis B. As IVIG may cause false positive hepatitis serology, monthly PCR testing is not required in subjects who are currently receiving or received prophylactic IVIG within 3 months before study enrollment and have a documented negative anti-HBc test before the initiation of IVIG therapy. PCR testing should be performed when clinically indicated (e.g., in the setting of rising transaminase levels).

Subjects with a known history of hepatitis C or who are hepatitis C antibody positive should be excluded from study.

4.1.14 Immune Phenotyping and Translational Analyses

For the phase 2-part, extensive immune phenotyping and assessment of in vitro full blood response to standardized stimuli will be tested. Part of these test will be performed locally according to the laboratory manual.

4.1.15 Biomarker Studies and Central Biobanking

Blood samples will be used for PD testing including, but not limited to, BTK occupancy, B-cell activation, MDSCs, and T-cell activation, cytokine analysis, and for further characterization of circulating tumor cells, lymphocyte and myeloid cell subsets and cell free DNA as well as immune phenotyping, NGS sequencing for recurrent mutations along with functional and genetic characterization of tumor cells and microenvironmental cells. Bone marrow biopsies/aspirates and tissue sections from archival tumor biopsies and/or any newly obtained biopsies performed during the study will be used for exploratory biomarker studies (including, but not limited to, expression of

BTK, characterization of disease subtype, and evaluations of MDSCs and activated CD8⁺ cells). Microbiome samples like feces, saliva, skin swabs and buccal swabs will be obtained for assessment of microbiome by shot gun and 16S sequencing.

4.1.16 Pharmacokinetic Analyses

Blood samples will be used for PK testing including but not limited to acalabrutinib and venetoclax concentrations at various time points post-dose on cycle 3 day 1 as detailed in appendix 1.

4.1.17 Tumor Assessments

A pretreatment computerized tomography (CT) scan with contrast (unless contraindicated) is required of the chest, abdomen, and pelvis and any other disease sites within 42 days before randomization.

End of treatment CT scans with contrast (unless contraindicated) of the chest, abdomen, and pelvis and any other disease sites will be done for tumor assessments 8 weeks (+/- 7 days) after last dose of drug (20 weeks after first dose of drug or start of observation). At all other visits, tumor assessments will be done by physical exam and laboratory results.

At suspicion of progression and/or prior to any new CLL treatment, CT scans with contrast (unless contraindicated) of the chest, abdomen, and pelvis and any other disease sites will be done for tumor assessments along with bone marrow biopsy and/or tissue biopsy. Specimens and biobank samples will be sent for central biobanking.

4.2 ASSESSMENT OF RESPONSE TO TREATMENT

Response assessments will be evaluated based on IWCLL 2018 Criteria (Hallek et al., Blood 2018), see appendix 8.

4.3 TREATMENT TERMINATION AND SAFETY FOLLOW-UP VISITS

A treatment termination (TT) visit is required for safety assessments for any subjects who permanently discontinue study drug for any reason, including disease progression. The TT visit should be scheduled within 7 days of the last dose of study drug, if possible, and is not required for subjects who discontinue from the study within 10 days of a scheduled study visit.

Each subject should be followed until the safety follow-up (SFU) visit at 2 years after his or her first dose of study drug or observation to monitor for resolution or progression of AEs and to document the occurrence of any new events, regardless of whether the subject receives a new CLL therapy or demonstrates disease progression within this timeframe. Subjects who withdraw consent for study treatment should still be encouraged to complete the SFU assessments, but these assessments cannot be mandated if subject consent for further study participation is withdrawn

The Schedule of Assessments (Appendix 1) describes the procedures required for the TT and SFU visits.

4.4 FOLLOW-UP FOR INFECTION, PROGRESSION AND SURVIVAL

4.4.1 Discontinuation Follow-up

Each subject should be followed until disease progression or the start of alternative CLL therapy and at least for the first two years after randomization. If neither of these has occurred at the time of the 2-year SFU visit, follow-up visits should occur approximately every 6 months until disease progression or next CLL treatment. During this period, subjects will be followed via out-patient clinic and/or registries per investigator discretion including registration of any infectious events.

4.4.2 Long-Term Follow-up

Once subjects progress or start use of alternative CLL therapy—for all subjects who have not withdrawn consent — they will be contacted or followed approximately every 3 months by clinic visit, electronic assessment or telephone, to assess survival, the use of alternative CLL therapy and infections.

4.4.3 Follow-up for Patients Assessed as Low Risk or Low Confidence by CLL-TIM

Patients assessed as low risk or low confidence prediction by CLL-TIM will be followed 6-monthly for assessment of infectious events, CLL treatment and overall survival by medical record review and/or registries. These patients are considered part of the screening cohort for the study, but not part of the clinical trial. Outcome data for this patient population will thus only be followed for assessment of the predictive performance of CLL-TIM and for comparison to the clinical trial population – no study specific procedures will be performed for this population, which will not be considered part of the trial.

4.5 MISSED EVALUATIONS

Missed evaluations should be rescheduled and performed as close to the original scheduled date as possible. An exception is made when rescheduling becomes, in the investigator's opinion, medically unnecessary because it is too close in time to the next scheduled evaluation. In that case, the missed evaluation should be abandoned.

5. STATISTICAL METHODS OF ANALYSIS

5.1 GENERAL CONSIDERATIONS

The study is designed as a phase 2 study with an optional subsequent extension to a phase 3 study that can be considered if the conditions detailed below are met. Patients enrolled in the

phase 2 study will be included in the optional phase 3 study if the decision is made to extend the study. As the primary outcome for phase 2 is prior to and different from the primary outcome in the optional phase 3 part, this should not affect the power for the phase 3 study. Randomization is between observation and pre-emptive treatment with acalabrutinib and venetoclax for 3 months. Based on the CLL-TIM algorithm, newly diagnosed CLL patients with high (>65%) risk of severe infection and/or treatment within 2 years from diagnosis can be identified. Approximately 20% of newly diagnosed CLL patients will fall into this high-risk group.

5.2 MISSING DATA HANDLING

No imputation of values for missing data will be performed except that missing or partial start and end dates for AEs and concomitant medication will be imputed according to prespecified, conservative imputation rules. Subjects lost to follow-up (or drop out) will be included in statistical analyses to the point of their last evaluation.

5.3 ENDPOINT DATA ANALYSIS

5.3.1 Safety Endpoint(s) for the Phase 2 Part as Primary Endpoint

- Grade ≥3-Infection-free survival 24 weeks after treatment initiation. This is a non-inferiority analysis as detailed in statistical analysis plan to assure safety of the combination treatment in this preemptive trial population.
- Rate and CTCAE grade of infections
- Treatment related adverse events, type, frequency and severity during and for 2 years after treatment

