3.9 DURATION OF THERAPY

Duration of treatment with acalabrutinib and venetoclax is for 3 cycles of 28 days; the end of trial is defined as seven years after start of treatment or observation with close follow up for the first two years, while follow up for AESI's, CLL treatment and survival continues until end of trial. The primary endpoint for the phase 2 part is 6 months after start of treatment or observation.

3.10 DOSING DELAYS AND MODIFICATIONSIn the case of AEs attributed to both acalabrutinib and venetoclax, the local investigator should decide whether dose

modifications apply to one or both drugs in collaboration with the sponsor, as no data on pharmacokinetic interaction between acalabrutinib and venetoclax are currently available.

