4.1.3 Adverse Events

An adverse event (AE) is any untoward medical occurrence in a patient or clinical study subject administered a medicinal product and which does not necessarily have a causal relationship with the treatment.

An AE can therefore be any unfavorable and unintended sign (including an abnormal laboratory finding), symptom, or disease temporally associated with the use of a medicinal (investigational) product, whether or not related to the medicinal (investigational) product.

Only information about AE's > grade 1 will be collected, unless the AE qualifies as an AESI or a SUSAR as detailed below.

Adverse event of special interest (AESI)

Atrial fibrillation, ventricular arrhythmias, tumor lysis events, infections, disease progression, treatment for CLL, malignancies and bleeding events are adverse events of special interest in this trial and will be actively requested for.

Serious adverse event (SAE)

A serious adverse event is defined as any untoward medical occurrence or effect that at any dose:

- Results in death
- Is a life-threatening event (i.e. the patient was at immediate risk of death at the time the reaction was observed)
- Requires hospitalization or prolongation of an existing hospitalization
- Results in significant or persistent disability or incapacity

- Is a congenital anomaly or birth defect
- Is an important medical event (i.e. important adverse events that are not immediately life threatening or do not result in death or hospitalization but may jeopardize the patient or may require intervention to prevent one of the above characteristics/consequences, including suspected transmission of infectious agents by a medicinal product).

Note: Clinical TLS is *an important medical event* in this trial which must be reported as SAE. SAEs must be reported to the sponsor through the eCRF system, which automatically notifies the sponsor, within 24 hours of awareness. The sponsor must notify within the defined timelines health authorities and the companies providing investigational drugs according to EU regulations.

Suspected unexpected serious adverse reaction (SUSAR)

All **suspected** Adverse Reactions which occur in the trial and that are both **unexpected** and **serious**.

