6.1.1 Adverse Event Reporting Period

The AE reporting period for this study begins when the subject receives the first dose of study drug or Cycle 1 Day 1 for the observation arm of the study and ends with the SFU visit.

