Appendix 4. Adverse Event Assessment of Causality

Is there a reasonable possibility that the event may have been caused by study drug? No___ Yes___ The descriptions provided below will help guide the principal investigator in making the decision to choose either "yes" or "no":

No = There is no reasonable possibility that the event may have been caused by study drug.

The adverse event:

- may be judged to be due to extraneous causes such as disease or environment or toxic factors
- may be judged to be due to the subject's clinical state or other therapy being administered
- is not biologically plausible
- does not reappear or worsen when study drug is re-administered
- does not follow a temporal sequence from administration of study drug

Yes = There is a reasonable possibility that the event may have been caused by study drug.

The adverse event:

- follows a temporal sequence from administration of study drug
- is a known response to the study drug based on clinical or preclinical data
- could not be explained by the known characteristics of the subject's clinical state, environmental or toxic factors, or other therapy administered to the subject
- disappears or decreases upon cessation or reduction of dose of study drug
- reappears or worsens when study drug is re-administered

<< Include any applicable response criteria, etc. as separate Appendices>>

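### The adverse-event endpoint counts only treatment-related events, so it gives no between-arm estimate of non-infectious toxicity, and its window runs 12 weeks past general adverse-event reporting

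*Protocol*

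**What the plan says.** Protocol Section 5.3.1 lists three safety endpoints for the phase 2 part. The first is grade ≥3 infection-free survival at 24 weeks, the second is the rate and grade of infections, and the third is "Treatment related adverse events, type, frequency and severity during and for 2 years after treatment". The synopsis and Section 2.2 carry the third item as a secondary objective in the same terms.

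Appendix 4 makes relatedness a yes/no judgement. Yes means: "There is a reasonable possibility that the event may have been caused by study drug". The comparator is observation without study drug.

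Collection is wider than this endpoint:

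- Section 4.1.3 defines an adverse event as one "which does not necessarily have a causal relationship with the treatment". It restricts collection to events above grade 1, except AESIs and SUSARs.
- Section 6.1.2 has all adverse events and serious adverse events recorded, with suspected relationship as one of several descriptors.
- Section 6.1.1 starts the reporting period at "first dose of study drug or Cycle 1 Day 1 for the observation arm of the study and ends with the SFU visit".
- Section 4.3 places the "safety follow-up (SFU) visit at 2 years after his or her first dose of study drug or observation".
- Section 3.9 states: "Duration of treatment with acalabrutinib and venetoclax is for 3 cycles of 28 days". It continues AESI follow-up to the end of the trial, seven years after the start of treatment or observation.

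**The concern.** These patients would not normally be treated, so the safety question is how much toxicity pre-emptive treatment adds to what observation alone would show. A count restricted to drug-related events cannot answer it, because only one arm can have such events. The count also depends on an investigator who knows the allocation deciding whether an event comes from the drug or from the disease. The synopsis and Section 6 acknowledge that this separation is difficult.

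Infections escape the problem because the other two endpoints in Section 5.3.1 have no relatedness filter. Non-infectious toxicity does not escape it. Sections 1.4.2 and 1.6.3 flag hemorrhage, atrial fibrillation, cytopenias and second malignancies as drug risks, yet in Section 5.3.1 the related-only endpoint is the only one that reaches them.

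The time window adds a second fault. It is anchored on the end of treatment, which the observation arm does not have, and it extends beyond the reporting period set in Sections 4.3 and 6.1.1. Safety findings feed the decision on phase 3 in Section 5.4, so the endpoint should measure what that decision needs.

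**Working it through.** **Which arm can contribute**

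| Event class | Relatedness filter in the stated endpoint | Recorded in the observation arm | Between-arm contrast from the endpoint as defined |
|---|---|---|---|
| Infections | none (first two items of 5.3.1) | yes | yes |
| Non-infectious events | yes (third item of 5.3.1) | yes (4.1.3, 6.1.1, 6.1.2) | no |

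The observation arm's count of related events is zero by definition, whatever its true event rate.

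**Timeline**

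1. Treatment length (Section 3.9): 3 × 28 days = 84 days; 84 / 7 = 12 weeks.
2. Check against the plan's own time points. The primary time point is 12 weeks after finishing treatment: 12 + 12 = 24 weeks, as stated in the synopsis. The CT scan is 8 weeks after the last dose: 12 + 8 = 20 weeks, as stated in Section 4.1.17. Both reproduce.
3. End of the endpoint window: 12 + 104 = week 116 after first dose, taking 2 years as 104 weeks.
4. End of general adverse-event reporting (Sections 4.3 and 6.1.1): week 104.
5. Uncovered: 116 − 104 = 12 weeks, and 12 / 104 = 11.5% of the stated post-treatment window.
6. Covered: 104 − 12 = 92 weeks; 92 / 104 = 88.5%; 92 × 7 / 30.4375 = 21.2 months instead of 24.
7. For AESIs the uncovered part is zero, because their follow-up runs to year 7. Bleeding, atrial fibrillation, ventricular arrhythmias and malignancies are AESIs (Section 4.1.3). Cytopenias are not, so the gap applies to them.

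Section 6 describes the treatment period for the DSMB's safety split as the first 6 cycles, against 3 in the synopsis and Section 3.9. These passages must be reconciled. On 6 cycles the same sum gives 6 × 28 / 7 = 24 uncovered weeks.

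**What a between-arm difference would deliver**

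The protocol gives no expected rates for non-infectious events in this population, so the rates below are assumptions. With 25 patients per arm, the 95% interval is d ± 1.96 × √[p₁(1 − p₁)/25 + p₀(1 − p₀)/25].

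| Treatment | Observation | Difference | 95% interval |
|---|---|---|---|
| 30% | 10% | 20 points | −1.5 to 41.5 |
| 40% | 20% | 20 points | −4.8 to 44.8 |
| 60% | 30% | 30 points | 3.7 to 56.3 |

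The estimate would be imprecise, but it would be a randomised one.

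**The case against.** The strongest reply is that nothing is lost. Events are collected without regard to cause in both arms over the same two years, and Section 3.4.2 aligns follow-up to avoid registration bias. A table of related events in the treated arm is an ordinary tolerability summary, and between-arm tables are usually left to the statistical analysis plan, which is not at hand.

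Much of this stands, and it rules out three stronger readings:

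- A reader might infer that excess toxicity cannot be estimated. The documents do not support that: the data for the estimate are collected.
- A reader might infer that follow-up fails to cover the endpoint. Only the last 12 of 104 post-treatment weeks are uncovered, and only for non-AESI events.
- A reader might apply the plan's 10% rate of grade ≥3 infection and picture a table showing 10% against 0% with no true difference. That uses the event class already compared without attribution. It also supposes that every infection is blamed on the drug, although Appendix 4 directs a negative answer where the disease or the patient's clinical state may explain the event.

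What does not stand is the appeal to the analysis plan. The point is not a missing table. The protocol itself states an endpoint and a window that leave out one arm and disagree with its own reporting period. Further tables elsewhere would not change the stated objective.

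One practical objection also holds. Appendix 1 has weekly ramp-up visits in cycle 1 (C1D8, C1D15, C1D22) for the treatment arm only. A plain between-arm count would therefore carry unequal ascertainment early on.

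**Conclusion.** The point holds as a fault of definition. As written, the adverse-event endpoint yields no between-arm estimate of non-infectious toxicity, depends on attribution by an investigator who knows the arm, and names a window ending 12 weeks after general reporting stops. The conclusion rests on three readings: relatedness as defined in Appendix 4, no study drug in the observation arm, and 12 weeks of treatment. It does not depend on any assumed event rate. The primary infection comparison is unaffected. The correction is worth making because the better endpoint uses data the protocol already collects, although 25 patients per arm will give wide intervals.

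**What to change.** In the synopsis, Section 2.2 and Section 5.3.1:

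1. Define the endpoint as all collected adverse events (grade 2 or higher, plus AESIs and SUSARs of any grade) by arm, regardless of relatedness, with type, frequency, severity and the between-arm difference with its interval.
2. Set the window from cycle 1 day 1 to 2 years after cycle 1 day 1 in both arms, in agreement with Sections 4.3 and 6.1.1.
3. Keep investigator-attributed related events as a supplementary table for the treatment arm.
4. Report grade ≥3 and serious events separately, since they are less sensitive to visit frequency, and state that cycle 1 ascertainment is unequal.
5. Reconcile the number of cycles given for the treatment period in Section 6 with the synopsis and Section 3.9.

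The cost is a change of wording in a few places and one additional table. No new data or visits are needed.

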5.3.2 Study Treatment Administration and Compliance

Descriptive information will be provided regarding the number of acalabrutinib and venetoclax doses prescribed, the total number of doses taken, the number of days of treatment, and the number and timing of prescribed dose delay, reductions and interruptions.

For each subject, acalabrutinib and venetoclax compliance will be described in terms of the proportion of study drug actually taken.

